#### **5. STUDY TREATMENTS**

Subjects will be randomized into one of 2 parallel groups:

- Bococizumab 150 mg subcutaneously every 2 weeks (n=100);
- Bococizumab placebo subcutaneously every 2 weeks (n=100);

## **5.1. Allocation to Treatment**

Each subject will receive a 4 digit identification number at the screening visit. A randomization scheme will be prepared for each study site. The pharmacist at each site will assign blinded study drug according to the randomization scheme. Subjects will self-inject (or if unable to self-inject, receive an injection by a home care giver) 150 mg of bococizumab or bococizumab placebo subcutaneously every 2 weeks. Subjects eligible to be randomized will be assigned a randomization number at week 0 (visit day 1). The randomization will be stratified by statin use. Each subject will receive 26 subcutaneous injections over the period of 52 weeks.

Subjects should adhere to their treatment schedule even if their scheduled clinic visit is rescheduled or missed due to unforeseen circumstances.

## **5.2. Drug Supplies**

### **5.2.1. Formulation and Packaging**

Bococizumab is presented as a sterile solution for subcutaneous administration, packaged in a glass pre-filled syringe (PFS) with a fixed needle. Each PFS contains a sufficient amount of bococizumab to provide the intended dose of drug at a concentration of 100 mg/mL. Each syringe contains bococizumab in an aqueous buffered solution.

Placebo is presented as a sterile solution for subcutaneous administration, packaged in a glass PFS with a fixed needle for subcutaneous administration. Each syringe contains an aqueous buffered solution.

Each PFS is for single use only.

### **5.2.2. Preparation and Dispensing**

Bococizumab and placebo will be provided in PFS packaged in cartons with tamper evident seals. The cartons should not be opened until the drug is to be administered. Drug will be dispensed to subjects in the sealed cartons.

### **5.2.3. Administration**

The drug may be injected into either an upper or lower quadrant of the abdominal wall, anterior aspect of the thigh or to the lateral aspect of the upper arm. Study staff, caregivers and subjects should refer to the Subject Study Medication Dosing Booklet and Instruction for specific instructions on the handling and administration of study drug and placebo.

### **5.2.4. Compliance**

Subjects will record their injections in a diary and all injections and dates will be collected in a data collection instrument (case-report form).

### **5.3. Drug Storage**

All bococizumab should be stored at 2 to 8° centigrade and protected from excessive shaking. Syringes should remain in the protective carton until the time of dosing. Storage conditions stated in the single reference safety document (Investigator Brochure) will be superseded by the label storage.

The investigational products must be stored as indicated. Deviations from the storage requirements, including any actions taken, must be documented and reported to Pfizer.

### **5.4. Concomitant Medication(s)**

All subjects will be questioned about HIV and CV concomitant medications (from now on designated as medications) at each visit.

Subjects should take prescribed permitted concomitant medication, as needed, prior to the clinic visit, if it can be administered with water only. Subjects taking a statin should remain on the same dose of the same statin throughout the study. In general, subjects should remain on stable dosages of concomitant medications throughout the study. Changes in doses are allowed if clinically indicated.

## **6. STUDY PROCEDURES**

Subjects will be required to fast prior to all study visits. Subjects who do not fast will be required to return for fasting laboratory tests, at the earliest possible time, before the next scheduled study visit.

### **6.1. Screening Visit**

#### **6.1.1. Visit Day**

The following procedures and activities will be performed during this visit:

Obtain written informed consent, obtain and record cardiovascular risk factors and cardiovascular medical history, Obtain and record demographics and general medical history, Measure and record vital signs: heart rate (HR), temperature and BP (Section 7.2.5), Conduct physical examination (Section 7.2.7), Obtain and record prior medications and instruct subjects on the use of concomitant medications (Section 5.5), Conduct 12-lead ECG test (Section 7.2.4), Verify trial eligibility by checking and documenting inclusion and exclusion criteria (Section 4.1, Section 4.2).

Collect specimens for laboratory exams:

- Blood for hematology and chemistry
- Urinalysis for toxicology screen (if necessary);

Provide lifestyle and contraception recommendations (Section 4.4.1);

Do practice injection with placebo to ensure patient is comfortable self-injecting;

Determine if subject meets ACC/AHA criteria for statin therapy.

- If subject meets criteria and is not currently on statin therapy, the subject will be referred back to their PCP.

## **6.2. Treatment Period**

### **6.2.1. Visit Day 1**

Visit day 1 will usually require up to 7 days to complete because of the requirement to perform the brachial artery reactivity flow-mediated dilation, coronary CT angiography, and FDG-PET/CT studies after randomization and before the first treatment.

A qualified FDG-PET/CT and coronary CT angiography interpreter will measure the images. Study drug dispensing will be delayed until after the repeat scan is completed.

Randomization:

Perform brachial artery reactivity flow-mediated dilation study;

Perform FDG-PET/CT imaging;

Perform coronary CT angiography;

Drug dispensation and dosing:

Instruct subject to self-inject;

Assessment during and after subject self-injection or injection by trained study nurse:

Provide lifestyle and contraception recommendations (Section 4.4.1);

### **6.2.2. Visit Days 29, 57, 85, 169, 211, and 281**

The following procedures and assessments should be made before subject self-injection:

Review results from laboratory values;

Measure and record vital signs: heart rate (HR), temperature and BP (Section 7.2.5);

Obtain and record on-going medications and instruct subjects on the use of concomitant medications (Section 5.5);

Inquire for and record adverse events;

Collect specimens for laboratory exams:

Provide diet and therapeutic lifestyle and contraception recommendations (Section 4.4.1);

Administer optional depression questionnaire;

Drug dispensation and dosing

### **6.2.3. Visit Day 365/End of Study Visit (EOS) ( $\pm 3$ days)**

The following procedures apply to subjects attending for Visit Day 365 or an early discontinuation visit if subjects choose to discontinue participation before Day 365. As detailed in Subject Withdrawal (Section 6.4) every effort should be made to ensure that all subjects complete study participation. Subjects who discontinue study treatment will be encouraged to continue participation in the study and complete all protocol assessments/evaluations. If, however, subjects choose not to continue attending study visits subjects should be encouraged to attend an EOS Visit and the follow up visits if indicated.

Review results from laboratory values;

Measure and record vital signs: heart rate (HR), temperature and BP (Section 7.2.5);

Conduct 12-lead ECG test (Section 7.2.4);

Obtain and record on-going medications and instruct subjects on the use of concomitant medications (Section 5.5);

Inquire for and record adverse events;

Collect specimens for laboratory exams:

Provide lifestyle and contraception recommendations (Section 4.4.1);

Administer optional depression questionnaire;

Collect all used and unused pre-filled syringe cartons.

### **6.3. Follow-up Visit**

A follow up visit will be arranged for all randomized subjects, including those who discontinued early in which case the follow up visit will occur 42 days after EOS Visit.

#### **6.3.1. Visit Day 407 ( $\pm 3$ days)**

Review results from laboratory values;

Measure and record vital signs: heart rate (HR), temperature and BP (Section 7.2.5);

Obtain and record on-going medications and instruct subjects on the use of concomitant medications (Section 5.5);

Inquire for and record adverse events;

Collect specimens for laboratory exams:

Provide lifestyle and contraception recommendations (Section 4.4.1);

Administer optional depression questionnaire.

## **7. ASSESSMENTS**

Every effort will be made to ensure that the protocol required tests and procedures are completed as described. However it is anticipated that from time to time there may be circumstances, outside of the control of the investigator that may make it unfeasible to perform the test. In these cases the investigator will take all steps necessary to ensure the safety and well-being of the subject.

### **7.1. Efficacy**

#### **7.1.1. Lipids**

Efficacy will be based on the percent change from baseline in fasting lipids, primarily LDL-C. Other lipid efficacy measures will include TC, HDL-C, non-HDL-C, TG, ApoB, ApoA-I, and Lp(a).

The investigators and clinical staff and the subject will remain blinded to lipid results for the duration of the study.

A DMC review will be implemented on all patients with LDL-C levels  $\leq 25$  mg/dL.

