## **SCHEDULE OF ACTIVITIES**

The Schedule of Activities table provides an overview of the protocol visits and procedures. Refer to STUDY PROCEDURES and ASSESSMENTS sections of the protocol for detailed information on each procedure and assessment required for compliance with the protocol.

The investigator may schedule unplanned visits in addition to those listed on the schedule of activities, in order to conduct evaluations or assessments required to protect the wellbeing of the subject

Study Phase	Screen	Rand	Treatment								Follow- Up
Protocol Activity (Week)	-8	0	4	8	12	24	30	40	52/EOS a		58
Visit Day	-57	1	29	57	85	169	211	281	365		407
Informed consent	X										
CV risk factors, demographics, medical history	X										
Vital Signs (HR, BP, temperature)	X	X	X	X	X	X	X	X	X		X
Height and weight		X				X		X	X		X
Physical examination	X					X		X	X		X
Prior Medications	X										
Concomitant medication		X	X	X	X	X	X	X	X		X
Adverse events		X	X	X	X	X	X	X	X		X
ECG	X					X					X
Review inclusion/exclusion criteria	X	X									
Laboratory											
Fasting Lipid Profile	X	X	X	X	X	X	X	X	X		X
Diet and contraception advice	X	X	X	X	X	X	X	X	X		X
Instruction on self-injection	X	X									
Randomization		X									
Dispense study treatment		X	X	X	X	X	X	X			
Brachial artery FMD		X,X				X					
FDG-PET/CT			X b				X b				
Coronary CT angiography			X b							X b	

a. EOS = End of Study, procedures to be completed for subjects who have early study discontinuation. Visit day 365/EOS will usually require 2 days to complete because of the requirement to perform coronary CT angiography study

b. FDG-PET/CT or coronary CT angiography reimage within 7 days if deemed necessary

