### **1.2.6. Benefits and Risks of Participation**

The benefit of participation in this study for all subjects is close monitoring of their medical condition and safety of their treatment. Those randomized to the active treatment group may benefit from lowering their LDL-C. Those randomized to the placebo group are not expected to obtain any additional benefit, beyond close monitoring of their medical condition and safety of their treatment, which may itself be associated with improving lipid levels. A potential risk of participation, for all subjects, is the occurrence of injection site reactions. For those receiving active treatment, there may be an additional risk of achieving a very low LDL-C. It is not known if there are any risks associated with very low LDL-C.

Complete information for this compound may be found in the bococizumab Investigator's Brochure.

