- (a) Coronary artery disease (CAD): prior MI due to atherosclerosis, coronary artery bypass graft surgery, percutaneous coronary intervention, or angiographic CAD with luminal diameter stenosis of at least one coronary artery at least 50%.
- (b) Cerebrovascular disease: prior ischemic stroke of carotid origin, carotid endarterectomy or stenting, or angiographic carotid stenosis of at least 50%.
- (c) Peripheral arterial disease: prior lower extremity arterial surgical or percutaneous revascularization procedure, or angiographic lower extremity arterial stenosis of at least 50%.

OR any one of the following CVD risk factors:

- (a) Controlled type II diabetes mellitus ( $\text{HbA1C} \leq 8.0\%$  within the past 90 days prior to study entry, regardless of use of medications)
- (b) Family history: a first degree relative who had a heart attack, stroke, or documented CVD as defined in the previous section that occurred:
  - a. When they were age 55 years or younger for males (father, uncle, or brother)
  - b. When they were age 60 years or younger for females (mother, aunt, or sister)
- (c) Current smoking: participant report of smoking at least a half a pack of cigarettes a day, on average, in the past month.
- (d) Hypertension: two consecutive BP readings with either systolic  $>140$  mmHg or diastolic  $> 90$  mmHg; or currently on antihypertensive medications.
- (e) Dyslipidemia: defined as or  $\text{HDL-C} \leq 40$  mg/dL for men or  $\leq 50$  mg/dL for women, regardless of medication use; or currently on lipid lowering medications.
- (f) A  $\text{hsCRP} \geq 2$  mg/L at screening.

8. Lipids at screening visit:

- Fasting  $\text{LDL-C} \geq 70$  mg/dL (1.81 mmol/L);
- Fasting  $\text{TG} \leq 600$  mg/dL (6.78 mmol/L).

9. If subjects meet ACC/AHA criteria for statin therapy and are not currently on a statin, subjects must be taking a stable dose of statin for at least 4 weeks, unless they are statin intolerant, refuse to take a statin, or have a medical condition (e.g. chronic hepatitis) where a statin is contraindicated.

10. Male and female subjects of childbearing potential must agree to use a highly effective method of contraception throughout the study and for at least 63 days after

the last dose of assigned treatment. A subject is of childbearing potential if, in the opinion of the investigator, he/she is biologically capable of having children and is sexually active.

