11. Current history of alcoholism or drug addiction according to the Diagnostic and Statistical Manual of Mental Disorders (DSM) IV criteria within 12 months prior to screening. Use of any illicit drug confirmed by urine toxicology test at screening that would in the opinion of the investigator interfere with study procedures or results.
12. History of cancer within the last 5 years (except for cutaneous basal cell or squamous cell cancer resolved by excision, or cervical carcinoma in situ).
13. Any disease or condition that might compromise the hematological, renal, hepatic, pulmonary, endocrine, central nervous, immune, or gastrointestinal systems (unless deemed not clinically significant by the Investigator and/or the Sponsor) or confound the interpretation of the study results. Examples of such conditions include but are not limited to nephrotic syndrome, uncontrolled diabetes, excessive alcohol consumption, cholestatic liver disease, unstable mental illness.
14. Undergoing apheresis or have a planned start of apheresis.
15. Initiation of or change in non-lipid lowering prescription drugs, herbal medicine or supplements (including foods with added plant sterols and stanols) within 6 weeks of screening with the exception of initiation or change in multivitamins used for general health purposes. Short-term use of medications to treat acute conditions, and vaccines are allowed (e.g., antibiotics or allergy medication).
16. History of allergic or anaphylactic reaction to any therapeutic or diagnostic monoclonal antibody (IgG protein) or molecules made of components of monoclonal antibodies (e.g., Enbrel® which contains the Fc portion of an antibody or Lucentis® which is a Fab).
17. Any abnormal hematology values, clinical chemistries, or ECGs at screening judged by the Investigator as clinically significant, which could impact on subject safety, were the potential subject to be included in the study, or interfere with the interpretation of study results.
18. Active phase hepatitis. Stable patients with hepatitis B or C infection  $>2$  years before randomization are eligible.
19. Aspartate transaminase (AST) or alanine transaminase (ALT)  $> 5$  X ULN at screening.
20. Direct bilirubin  $> 4$  X ULN at screening.
21. Calculated fibrosis-4 score  $> 3.25$  (see section 7.2.1.1 for instructions on how to calculate).
22. GFR^1  $< 30$  mL/min/1.73m^2 at screening or undergoing dialysis.
23. Plans to donate blood during the study.

---

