### **8.2. Abnormal Test Findings**

The criteria for determining whether an abnormal objective test finding should be reported as an AE are as follows:

- Test result is associated with accompanying symptoms; and/or
- Test result requires additional diagnostic testing or medical/surgical intervention; and/or
- Test result leads to a change in study dosing or discontinuation from the study, significant additional concomitant drug treatment, or other therapy; and/or
- Test result is considered to be an AE by the investigator or sponsor.

Merely repeating an abnormal test, in the absence of any of the above conditions, does not constitute an AE. Any abnormal test result that is determined to be an error does not require reporting as an AE.

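### Section 7.1.1 keeps on-study triglyceride results from the site, and the protocol states no route for acting on a markedly raised value; a TG alert to the DMC would be a cheap safety improvement

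*Combined protocol and SAP*

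**What the plan says.** Section 7.1.1 lists TG with the other lipid efficacy measures and then states: "The investigators and clinical staff and the subject will remain blinded to lipid results for the duration of the study". It makes no exception for TG. The same section gives one lipid trigger: "A DMC review will be implemented on all patients with LDL-C levels" at or below 25 mg/dL. Section 1.2.6 shows the risk that this trigger addresses: "For those receiving active treatment, there may be an additional risk of achieving a very low LDL-C".

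The Schedule of Activities has a row "Fasting Lipid Profile" with post-randomization draws at weeks 4, 8, 12, 24, 30, 40, 52 and 58. Section 4.1, item 8, caps fasting TG at 600 mg/dL, at screening only.

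Two general provisions could bear on an abnormal value. The visit lists (for example Section 6.2.2) include "Review results from laboratory values". Section 8.2 makes a finding reportable if, among other grounds, "Test result is considered to be an AE by the investigator or sponsor".

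On who is blinded, the Study Design part of the Protocol Summary includes the sponsor. Sections 3 and 7.1.1 do not name the sponsor. Section 9.6 gives the DMC a general safety remit under a charter that is not among the documents, and its members include a lipid expert.

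**The concern.** The blinding rule protects LDL-C, which would reveal treatment. It also covers TG, so the site steps that would normally pick up an abnormal laboratory value cannot work for TG: staff cannot review, or judge to be an adverse event, a result withheld from them. The LDL-C trigger does not respond to TG.

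The population makes this worth a sentence. Section 1.2.1 describes high TG as common in HIV infection and cites 40% above 200 mg/dL on combination therapy with a protease inhibitor and 15% in untreated subjects. Subjects may enter with TG up to 600 mg/dL and are then followed for 58 weeks. At stake is the care of a few individuals, not the validity of a trial result.

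**Working it through.** **1. Text check.** For a markedly raised on-study TG without symptoms, each stated route gives:

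- Site review of laboratory values (Section 6.2.2 and later visits): blocked by 7.1.1.
- Abnormal-test rule (8.2): blocked for the investigator; open to the sponsor only if the sponsor can see lipids.
- LDL-C review (7.1.1): not triggered by TG.
- Safety tabulations (9.4): name hematology and blood chemistry, not TG, and summarize by group.
- General DMC review (9.6): possible, but its content is in the charter.

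**2. The plan's own power figure.** Section 9.1 uses 54 per group, SD 25%, two-sided alpha 0.05. With the phase II effect of 53.4 points, the normal approximation gives power of about 100%, which agrees with the stated 99% or more. The difference needed for 99% power is 25 × √(2/54) × (1.960 + 2.326) = 20.6 points.

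**3. Expected alerts.** The documents give no TG variance, so the following are assumptions: log-normal TG; total log-SD 0.5 to 0.7; within-subject log-SD 0.25 to 0.35; screening TG at or below 600; random variation only; and 15% or 40% of the source population above 200 mg/dL (the two figures in 1.2.1). Simulating 2,000,000 subjects per setting over eight visits and scaling to 200 gives:

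| Share above 200 mg/dL | Ever above 600 | Ever above 1000 |
|---|---|---|
| 15% | 0.6 to 3.4 | about 0.01 to 0.3 |
| 40% | 4.9 to 17.6 | about 0.1 to 2.1 |

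The 40% row is probably too high, because Section 4.2, item 13, gives as examples of excluded conditions "nephrotic syndrome, uncontrolled diabetes, excessive alcohol consumption, cholestatic liver disease, unstable mental illness", and item 10 excludes untreated hypothyroidism.

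**4. Worst-case cost to the endpoints.** Take the highest counts, put every alerted subject in the placebo arm (n = 100), and let each start a statin. Inputs: a 37% LDL-C fall (rosuvastatin 10 mg in HIV, 1.2.1); a 7% TBR change (Protocol Summary, Statistical Methods), assumed here for a statin; and 19.4 + 20.4 = 39.8 points for non-calcified plaque (1.2.4). The shift is alerts × effect / 100.

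| Endpoint | Limit 600 | Limit 1000 |
|---|---|---|
| Week 12 LDL-C (alerts by week 8) | 7.27 × 37/100 = 2.7 | 0.68 × 37/100 = 0.25 |
| Week 24 LDL-C (by week 12) | 9.71 × 37/100 = 3.6 | 0.97 × 37/100 = 0.36 |
| Week 24 TBR (by week 12) | 9.71 × 7/100 = 0.68 | 0.97 × 7/100 = 0.07 |
| Week 52 plaque (by week 40) | 15.0 × 39.8/100 = 6.0 | 1.71 × 39.8/100 = 0.7 |

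The 1000 mg/dL shifts are about one ninth to one eleventh of those at 600 (1.71/15.0 = 0.114; 0.68/7.27 = 0.094). For week 12 LDL-C, 53.4 − 2.7 = 50.7 points remain, far above the 20.6 needed.

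For FDG-PET, 200 × 0.90 × 0.92 × 0.92 = 152 are evaluable, or 76 per arm. A difference of 0.07 × 2.5 = 0.175 with SD 0.29 has power 0.961. At the 600 limit the difference falls to 0.175 × (1 − 0.0971) = 0.158, with power 0.919. If alerts split evenly and both arms respond alike, the net shift is about zero.

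**The case against.** The strongest objection is that silence in this text is weak evidence of a gap. The DMC Charter is unseen. The contents list carries subject withdrawal and dosing stopping criteria (6.4 and 6.4.1) with broken bookmarks, and Section 6.2.3 still refers to Section 6.4, which is not in the body. If Sections 3 and 7.1.1 are right and the sponsor is not blinded to lipids, the sponsor could use the rule in 8.2. All of this stands: the point can say only that no route is stated in the protocol text. A reader might infer that no safeguard exists; the documents do not support that.

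It is also fair that the documents name no on-study TG level that calls for action and estimate no harm. The entry ceiling is a level that the plan accepts, and under the model above an alert at 600 flags chance fluctuation, mostly in subjects already near it. This argues for a limit above 600, set by clinicians.

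Finally, a DMC that meets periodically does not help an individual unless someone receives the value quickly and is named to act. That stands, and the fix must provide for it.

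What the objection does not remove is that the blinding rule itself stops the site's stated steps from working for TG.

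**Conclusion.** The point holds as a cheap improvement with a small yield; it is not an error in the plan. Under the assumed variability, about 0 to 2 of 200 subjects would pass 1000 mg/dL and 0.6 to 18 would pass 600. These ranges rest on assumed log-SDs and on random variation alone.

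Three stronger readings should be resisted. First, a reader might infer that the LDL-C trigger is half of a lipid alert that forgot TG. Section 1.2.6 shows that it answers a separate risk specific to active treatment. Second, a reader might infer that bococizumab raises TG. Nothing in the plan says so. Third, a reader might infer a threat to the efficacy results. The primary LDL-C is measured by a direct method (9.2.1), and TG is already compared between arms at weeks 12 and 24 (9.2.3).

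Confidence is medium, because the DMC Charter and the sponsor's access to lipid results could each settle the matter.

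**What to change.** Add to Section 7.1.1:

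> The laboratory will promptly report any post-baseline fasting TG above a limit fixed before enrolment by the sponsor's clinicians (above the 600 mg/dL entry ceiling, for example 1000 mg/dL) to a named DMC member, within a stated number of days. That member may release the TG value alone to the site investigator for repeat testing and clinical action. All other lipid results stay blinded.

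Record any resulting therapy change with its date, and list the alerts by arm in the Section 9.4 outputs. If the DMC Charter already has such a limit, cite it in 7.1.1 instead. State in one place whether the sponsor is blinded to lipids, since the Protocol Summary and Section 3 differ.

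The cost is a few sentences, one laboratory alert and one line in a safety table. The downside is a few therapy changes against the stable-dose expectation in 5.4, and possible fibrate–antiretroviral interactions (1.2.1), which the treating clinician must weigh before adding a drug. Alpha, planned sample size and the primary analysis do not change.
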